1.1 Background and rationale

The availability of specialist health care is limited, and thus efficient management of available resources is needed. A promising approach for improving resource management is task shifting, where tasks are delegated from specialists to allied health professions. Tasks suitable for delegation need to be identified and the safety, effectiveness and cost efficiency of task shifting evaluated. This study evaluates the suitability of shifting the management of hand osteoarthritis (OA) from rheumatologist to occupational therapy (OT) specialists through a randomized controlled non-inferiority trial.

1.2 Trial Objectives

1.2.1 Primary Objective

The primary objectives of this study are to assess whether OT-led hand OA care is non-inferior to rheumatologist-led OA care with regards to the proportion of patients with disease improvement 6 months after the study visit, and whether OT-led hand OA care is more cost effective than rheumatologist-led care.

1.2.2 Secondary Objectives

To assess the characteristics of patients with hand OA referred to specialist health care with regards to a) joint affection, b) disease activity, c) symptoms and d) function as well as demographic features.

To identify predictors for symptom improvement 6 and 12 months after baseline.

1.2.3 Exploratory Objectives

To identify predictors for treatment response 6 and 12 months after baseline.

2 Trial Methods

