2.1 Trial Design

The TASKSHIFT study is designed as a randomized, controlled, multi-center, single-country, non-inferiority comparative study. Management allocation is a 1:1 ratio. Patients are randomised to either OT-led or rheumatologist-led care.

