5.2.1.4 Assumption Checks and Alternative Analyses

A logistic regression includes the following assumptions:

STATISTICAL ANALYSIS PLAN for TASKSHIFT

- Binary dependent variable: This assumption is fulfilled via the study design.
- Independence: This assumption is fulfilled via the study design.
- No severe multicollinearity: This assumption is fulfilled via the study design.
- Sufficient number of observations: We are expecting a rate of approximately 35% responders, which would provide a sufficient number of patients per group.

5.2.1.5 *Missing Data*

We are expecting the amount of missing data to increase with time, but we cannot retrace the individual reasons for missingness. The primary analysis will be based on complete case analysis, whereas the cost-efficiency analysis will utilize imputation.

5.2.1.6 *Sensitivity Analyses*

If deemed necessary, sensitivity analyses will be conducted to address missing data, if needed also on subgroup data. Further, analyses adjusted for baseline status of disease activity, pain and function will be conducted to evaluate a possible effect on response rate within the two treatment arms.

5.2.1.7 *Subgroup Analyses*

No subgroup analyses are planned outside of the sensitivity analyses.

5.2.2 *Continuous Secondary Outcomes*

5.2.2.1 *Main Analysis*

To identify clinically relevant predictors for symptom improvement 6 and 12 months after baseline, we will fit a regression model and select variables based on standardized beta-values as well as clinical usefulness based previous research and clinical relevance.

5.2.2.2 *Summary Measures*

See 5.1.1

5.2.2.3 *Assumption Checks*

Regression models entail four key assumptions:

- Independence: Given the study design, we are confident that this assumption is met.
- Linear relationship: If this assumption is violated, we will apply a logarithmic transformation.
- Normality: If this assumption is violated, we will apply a logistic transformation

STATISTICAL ANALYSIS PLAN for TASKSHIFT

- Homoscedasticity: If this assumption is violated, we will apply a logistic transformation to the dependent variable or explore alternative options depending on the data characteristics.

5.2.2.4 *Missing Data*

Same as 5.2.1.4

5.2.2.5 *Sensitivity Analyses*

Same as 5.2.1.5

5.2.2.6 *Subgroup Analyses*

Same as 5.2.1.6

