5.2.3 Additional Analyses

5.2.3.1 *Exploratory Analyses*

The following additional, hypothesis-generating exploratory analyses will be conducted in addition to the above-stated analyses. If during the course of the data analyses additional questions will be raised, we will add them to this list of exploratory analyses.

- 1) To explore the potential influence of disease activity on treatment response, we will compare participants with erosive hand OA to those with less active inflammation, as defined by Xray scorings. Comparative analyses as well as additional regression models will be calculated for this.
- 2) To explore associations between different disease-related factors, we will investigate the relationships between various factors using correlation analyses.
- 3) To understand the disease trajectory of the participants, we will explore time and treatment dependent changes in different disease-related factors and compare these between the groups using comparative statistics and regression models.

6 Safety Analyses

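### SAP 5.2.2.1 selects predictors of improvement without fixing the outcome's baseline value, arm and centre in the model, so regression to the mean can decide what is selected

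*SAP*

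**What the plan says.** The SAP has two predictor objectives. The secondary one (1.2.2) is "To identify predictors for symptom improvement 6 and 12 months after baseline". The exploratory one (1.2.3) is "To identify predictors for treatment response 6 and 12 months after baseline".

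One method is given, in 5.2.2.1 under continuous secondary outcomes: "we will fit a regression model and select variables based on standardized beta-values", together with clinical usefulness judged from previous research and clinical relevance. The section does not define improvement, list the candidates, or say whether the outcome's baseline value, the randomised arm or the centre is always in the model.

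For the exploratory objective, 5.2.3.1 item 1 adds: "we will compare participants with erosive hand OA to those with less active inflammation, as defined by Xray scorings". It mentions further regression models without giving their terms, and the whole list is labelled hypothesis-generating.

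Adjustment for baseline pain, disease activity and function appears in 5.2.1.1 and 5.2.1.6, as a sensitivity analysis of the primary outcome. Section 5.2.2.5 refers back to 5.2.1.5 for sensitivity analyses, but 5.2.1.5 is the missing-data section. The reference seems to be off by one and meant for 5.2.1.6. Even read that way, baseline adjustment reaches the predictor analysis only as a sensitivity analysis.

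**The concern.** Improvement after baseline is most naturally a change score. The section heading says continuous, and the assumption checks in 5.2.2.3 concern normality and homoscedasticity, with transformation of the dependent variable. A change score contains the baseline value. A patient who scores badly at entry will on average score less badly later, whatever care is given, so the baseline score is associated with improvement through regression to the mean.

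Selection by size of standardised beta favours such a variable and anything correlated with it. Whether the model ends up adjusted for baseline then depends on the selection step and not on the plan. At stake is the content of the predictor list and how it is read. In a trial of who should manage hand OA, a list headed by baseline severity and described as predicting treatment response could be taken to show who gains from care, or who should see which provider. The model as stated supports neither reading.

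**Working it through.** **1. The plan's own figure.** SAP 2.3 gives no number for the predictor analyses, only the primary sample size. With 35% response in both arms, a 15-point margin, one-sided alpha 0.025 and 80% power:

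n = (1.96 + 0.8416)² × 2 × 0.35 × 0.65 / 0.15² = 158.7, so 159 per arm.

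Allowing for 20% drop-out, 159 / 0.8 = 198.75, so 199 per arm against 200 stated. The figure reproduces. It implies 400 × 0.8 = 320 completers, used below.

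**2. Baseline against improvement when care has no effect.** Let B be the baseline score and F the follow-up score, with equal variances and correlation r. The SAP gives no r, so a range is assumed. Then

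corr(B, B − F) = (1 − r) / √(2(1 − r)) = √((1 − r)/2).

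For the responder columns, one million patients were simulated per value of r. The cut-off on improvement was set so that 35% respond overall. This is a single-score stand-in for the OMERACT/OARSI rule, whose components the SAP leaves to the protocol.

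| Assumed r | Correlation of baseline with improvement | Response, lowest baseline quarter | Response, highest baseline quarter |
|---|---|---|---|
| 0.5 | 0.50 | 12.9% | 60.8% |
| 0.6 | 0.45 | 14.9% | 57.9% |
| 0.7 | 0.39 | 17.5% | 54.6% |
| 0.8 | 0.32 | 20.8% | 50.6% |
| 0.9 | 0.22 | 24.8% | 45.8% |

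**3. Would 320 completers show it?** By Fisher's transformation, at r = 0.9 (the weakest case): atanh(0.224) × √317 = 4.05; 4.05 − 1.96 = 2.09; probability 98%. It is higher at every smaller r.

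**4. Spill-over to other candidates.** Take a candidate X with correlation ρ to B and no further relation to F once B is known. Then corr(X, B − F) = ρ√((1 − r)/2), so X inherits the artefact in proportion to ρ if B is not in the model. If X also carries a truly worse prognosis, the two contributions have opposite signs and can partly cancel, hiding a real factor.

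**5. What including baseline does.** With B in a linear model, analysing F or B − F gives the same coefficients for all other terms, apart from sign. What matters is that B stays in, not which of the two outcomes is used.

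**6. What a predictor-by-arm term could show.** Assume 160 completers per arm, a marker present in half, and 35% response. The standard error of the interaction is √(4 × 0.35 × 0.65 / 80) = 10.7 points. The interaction detectable with 80% power is 2.80 × 10.7, about 30 points. Power is 15%, 29% and 47% for true interactions of 10, 15 and 20 points.

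**The case against.** The strongest reply is that this is a gap in specification and not an error. The SAP never says that improvement is a change score or that baseline, arm and centre are left out. Selection also uses clinical judgement. The artefact concerns the outcome's own baseline value and its correlates, so it need not touch factors unrelated to baseline. All of this stands, and it is why the conclusion is conditional. It does not remove the point: the modelling section of an SAP is where these terms belong, and the same SAP treats baseline pain, function and disease activity as relevant when it compares the arms.

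Four stronger readings may tempt a reader, and the SAP does not support them.

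- **That the objectives fail for want of an untreated arm or an arm interaction.** It is true that "Patients are randomised to either OT-led or rheumatologist-led care". But response in this SAP means OMERACT/OARSI responder status (2.4.3 and 5.1.2), so both objectives read naturally as prognostic questions, which need neither. Nor does the SAP propose to use the results to allocate patients.
- **That Table 1 shows most responders would respond without care.** Dividing its six-month control rates (27% to 32%) by the planned 35% does not show this. Those controls had treatment as usual, or were margins of a factorial trial that could include the other component. They are not shown to be untreated.
- **That the erosive comparison is coupled in the same way.** Erosive status is defined by X-ray and is not the baseline value of a symptom score.
- **That baseline severity is certain to be selected.** This depends on the outcome definition and the candidate list, and neither is given.

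**Conclusion.** The point holds as a minor one. SAP 5.2.2.1 selects predictors without naming any term that must stay in. If improvement is analysed as change from baseline, baseline severity and its correlates are liable to be selected through regression to the mean alone. The correlation of baseline with improvement would be about 0.50 to 0.39 for an assumed r of 0.5 to 0.7, and still 0.22 at r = 0.9. Coefficients of candidates related to baseline would be distorted.

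The size rests on equal variances at the two times, on the assumed range of r, and on improvement being a change score or a response derived from one. Leaving out arm matters less, because allocation is independent of baseline. Arm belongs in the model because two forms of management are pooled, and centre because case mix and outcome may differ between the two hospitals. The primary analysis, its decision rule and the sample size are not affected.

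**What to change.** In the main analysis of SAP 5.2.2.1:

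- Define improvement for each outcome and time point.
- Always include the outcome's baseline value, randomised arm and centre, as terms not subject to selection.
- For the responder outcome, always include baseline pain, function and disease activity in the same way.

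In 1.2.2, 1.2.3 and 5.2.3.1 item 1, describe main effects as prognostic factors under specialist care. State that they do not show who benefits from care or who should see which provider. A predictor-by-arm interaction is optional. If one is reported, give it with its confidence interval and label it exploratory, because it would be imprecise. Correct the cross-reference in 5.2.2.5 at the same time.

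The cost is a few sentences and a few model terms, using baseline data that the SAP already plans to use. The downside is that baseline severity is reported as an adjuster and no longer as a selected predictor.

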2.1 Trial Design

The TASKSHIFT study is designed as a randomized, controlled, multi-center, single-country, non-inferiority comparative study. Management allocation is a 1:1 ratio. Patients are randomised to either OT-led or rheumatologist-led care.

2.2 Randomisation

STATISTICAL ANALYSIS PLAN for TASKSHIFT

Eligible patients are allocated in a 1:1 ratio between OT-led and rheumatologist-led care, using two computer-generated randomization lists with a block size of 10, one for each participating center.

The randomization process is described in full within the clinical trial protocol. Details of the randomization including the final random allocation list are held securely and unavailable to unauthorized trial personnel.

2.3 Sample size

Based on an extensive literature review (Table 1), we have conservatively estimated the six-month response rate for rheumatologist-led care to be 35%. Responders are defined according to the OMERACT-OARSI criteria (3).

The non-inferiority margin is set to 15 percentage points. To ensure adequate statistical power, a sample size of 400 patients (200 per arm) is required. This calculation assumes 80% power that a two-sided 95% confidence interval will demonstrate that OT-led care is not more than 15 percentage points inferior to rheumatologist-led care, given a response rate of 35% in both groups.

An assumed drop-out rate of 20% has been included in the sample size determination, based on observed attrition rates in comparable studies, typically ranging from 20% to 25%. Randomization will be stratified by center to account for inter-site variability.

More detailed information is available in the study protocol (2).

Publication	Type of intervention	Control group	Proportion of responders (intervention/control)			
			4 weeks	3 months	6 months	12 months
Østerås 2014 (4)	Hand exercises	Treatment as usual		46 % / 16%	30% / 28%	
Hennig 2015 (5)	Hand exercises	Treatment as usual		43% / 6%		
Dziedzic 2015 (6)	Joint protection	No joint protection		28% / 22%	42% / 27%	34% / 27%
Dziedzic 2015 (6)	Exercises	No exercises		26% / 24%	36% / 32%	38% / 34%
Wenham 2012 (7)	Prednisolone	Placebo	57% / 57%			

Table 1: Overview of the literature review used to estimate the expected number of responders.

STATISTICAL ANALYSIS PLAN for TASKSHIFT

2.4 Statistical Framework

2.4.1 Hypothesis Test

This trial is designed to assess the non-inferiority of OT-led OA management compared to rheumatologist-led OA management with regards to disease improvement based on OMERACT/OARSI responder criteria (3) measured 6 months after the study visit.

The primary hypothesis test is:

- Null hypothesis: The probability of a patient fulfilling the OMERACT/OARSI responder criteria (3) at 6 months with OT-led management is at-least 15 percentage points below that of rheumatologist-led management.
- Alternative hypothesis: The probability of a patient fulfilling the OMERACT/OARSI responder criteria (3) at 6 months with OT-led management is no more 15 percentage points below that of rheumatologist-led management.

2.4.2 Additional analysis

This trial will also compare the cost effectiveness of OT-led OA management compared to rheumatologist-led OA management.

2.4.3 Decision Rule

Non-inferiority of treatment response rate is claimed if the null hypothesis is rejected on the significance level (alpha) of 0.025 (one-sided). That is, if the upper limit of the two-sided 95% confidence interval for the treatment difference (probability of response under RT minus OT management) is less than 15%.

2.5 Statistical Interim Analyses and Stopping Guidance

There will be no interim analyses in this trial.

2.6 Timing of Final Analysis

The main analysis is planned when all patients have concluded 182 days post baseline, all data have been entered, verified and validated and the primary database has been locked.

2.7 Timing of Outcome Assessments

Outcomes are assessed at a second visit 6 months after the primary visit. Additionally, they are reassessed via a mailed questionnaires 12 months after the primary visit.

Visit Label	Target Day	Definition (Day window)
V1. Screening	Day – 21 (app 3 weeks before BL assessment)	Day - 21

STATISTICAL ANALYSIS PLAN for TASKSHIFT

V1. Randomisation	Day – 21 (by project leader who randomised the participant and booked an appointment at either rheumatologist or OT, thereafter put the allocation information in a closed and sealed envelope, which was opened by the Research assistant after baseline assessment)	Day - 21
V1. Baseline	Day 0 Baseline assessment	Day 0
V2 Follow-up Last study visit	Day 182 Main outcome measurement timepoint	
Mail Follow-up	Day 364	

3 Statistical Principles

3.1 Confidence Intervals and p-values

See section 2.4

3.2 Adherence and Protocol Deviations

3.2.1 Adherence to Allocated Treatment

Only participation in the primary visit is registered as adherence, it is not registered whether suggestions/instructions are adhered to.

Non-adherence is defined as not participating in visit 1, and will be presented in the CONSORT diagram.

3.2.2 Protocol Deviations

Given the definition of adherence, no protocol deviations after visit 1 are registered. Please see the study protocol (2) for details regarding study design.

3.3 Analysis Populations

The Enrolled set will include all patients who have provided informed consent, have been included into the study data base, randomly assigned to one of the two groups and completed the first visit. Given the study design, the Enrolled set will be equal to the Full Analysis Set (FAS).

STATISTICAL ANALYSIS PLAN for TASKSHIFT

4 Trial Population

4.1 Screening Data, Eligibility and Recruitment

The total number of screened patients and reasons for not entering the trial will be summarised and tabulated.

A CONSORT flow diagram (details in study protocol (2)) will be used to summarise the number of patients who were:

- assessed for eligibility at screening
- eligible at screening
- ineligible at screening*
- eligible and randomised
- eligible but not randomised*
- received the randomised allocation
- lost to follow-up* 6 months
- lost to follow-up* 12 months

*reasons will be provided.

4.2 Withdrawal/Follow-up

The status of eligible and randomised patients at trial end will be tabulated by group according to

- completed intervention and assessments
- withdrew consent
- lost to follow-up

This will be presented in the CONSORT diagram.

4.3 Baseline Patient Characteristics

The patient demographics and baseline characteristics to be summarised include age in years, gender, marital status, education, occupational status, BMI, number of interphalangeal joints with bony enlargements, degree of hand OA (based on radiological assessment using the Kellgren Lawrence method), function, hand strength, duration of symptoms, comorbidities and medication, laboratory inflammation markers as well as site of treatment.

Patient demographics and baseline characteristics will be summarised by randomised treatment arm and overall using descriptive statistics (N, mean, standard deviation, median, 25/75 percentiles, minimum, and maximum) for continuous variables, and number and percentages of patients for

STATISTICAL ANALYSIS PLAN for TASKSHIFT

categorical variables. Any clinically important imbalance between the treatment groups will be noted.

5 Analysis

5.1 Outcome Definitions

5.1.1 General Definitions and Derived Variables

5.1.1.1 *Gender*

Dichotomized as “male/female”.

5.1.1.2 *Age*

Age in years

5.1.1.3 *Education*

Dichotomized into less than/more than 12 years.

5.1.1.4 *Civil status*

Living alone “yes/no”.

5.1.1.5 *BMI*

Body Mass Index (BMI) = Body weight in kilograms divided by the square of the height in meters.

5.1.1.6 *Function*

Based on the MAP-hand questionnaire. A mean score is calculated from the answers, at least 15 of 18 items must be answered

5.1.1.7 *Analgetics*

Dichotomized to “Usage yes/no”

5.1.1.8 *Duration of symptoms*

Duration in years

5.1.1.9 *Occupation status*

Dichotomized to “Is working yes/no”.

5.1.1.10 *Average hand strength*

Mean score for left and right hand separately, units are given in kg.

5.1.1.11 *Number of painful joints*

Sum score of both hands combined, has a maximum score of 30.

5.1.1.12 *Number of joints other than hand affected by OA*

Dichotomized into “yes/no”.

5.1.1.13 *Comorbidities*

Dichotomized into “yes/no” (Yes = one or more comorbidities).

STATISTICAL ANALYSIS PLAN for TASKSHIFT

5.1.1.14 Hospital

Which of the participating sites the patient was allocated to, coded as 1 or 2.

5.1.1.15 QALY

Quality-adjusted life years, calculated based on scores in the utility measure EQ-5D-5L.

5.1.2 Primary Outcome Definitions

The primary outcome treatment effectiveness will be defined as OMERACT/OARSI response (3) coded as yes/no. The outcome regarding cost efficiency will be defined using the utility measure EQ-5D-5L. Both scores are described in detail in the study protocol (2).

5.1.3 Secondary Outcomes Definitions

The number of painful joints, function (measured by the MAP-hand questionnaire) and hand strength (measured by JAMAR dynamometer) will be reported at baseline and 6 months. Information about adverse events will be collected from patients' medical records and used in the evaluation of safety.

5.1.4 Overview of Outcomes

Level	Outcome	Timeframe	Type
Primary	OMERACT/OARSI response (3)	182/364 days	Dichotomous
	EQ-5D-5L (8)	182/364 days	Discrete/Continuous
Safety	Adverse events	182 days	Discrete

5.2 Analysis Methods

5.2.1 Primary Outcome

5.2.1.1 Primary Analysis

For the analysis of the primary outcome, a logistic regression with treatment provider as independent and OMERACT/OARSI responder classification (3) as dependent variable will be conducted, adjusting for treatment center (the stratification factor used in the randomization). Response probability as well as risk difference will be calculated using the adjusted risk and risk difference estimators (9) using bootstrapping to estimate standard errors to form normal based 95%

STATISTICAL ANALYSIS PLAN for TASKSHIFT

confidence intervals. As a sensitivity analysis, an analysis will also be carried out adjusting for baseline pain, disease activity and function.

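### The primary non-inferiority model adjusts only for centre; moving the already planned baseline pain, disease activity and function covariates into it costs little and probably adds precision

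*SAP*

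**What the plan says.** The primary analysis (SAP 5.2.1.1) is a logistic regression of OMERACT/OARSI response on treatment provider, "adjusting for treatment center (the stratification factor used in the randomization"). The effect measure is an adjusted risk difference with a bootstrap standard error and a normal-based 95% interval.

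Adjustment for prognostic baseline variables is planned only as support: "As a sensitivity analysis, an analysis will also be carried out adjusting for baseline pain, disease activity and function". Section 5.2.1.6 repeats this: "analyses adjusted for baseline status of disease activity, pain and function will be conducted to evaluate a possible effect on response rate".

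The decision rule (2.4.3) uses the 15-point margin, and non-inferiority is claimed "if the upper limit of the two-sided 95% confidence interval for the treatment difference (probability of response under RT minus OT management) is less than" that margin.

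Other statements that bear on the point:
- Missing data (5.2.1.5): "The primary analysis will be based on complete case analysis".
- Function (5.1.1.6) is the mean MAP-Hand score, for which "at least 15 of 18 items must be answered".
- Drop-out (2.3) is taken as 20%, "based on observed attrition rates in comparable studies, typically ranging from 20% to 25"%.

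**The concern.** The interval that decides the trial comes from the less precise of two models that the SAP already intends to fit. If baseline pain, disease activity and function predict who responds, leaving them out of the deciding model gives a wider interval than the data allow.

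The design has almost no slack. It meets its 80% target at 20% drop-out with one completer per arm to spare, and 20% is the lower end of the attrition range that the SAP itself cites. Covariates that are already planned are the cheapest way to win back some precision.

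Two details stand in the way of simply exchanging the two models:
- **Undefined covariates.** Function has a definition, but the SAP does not say which variable represents pain or disease activity in this model. Section 5.1.1.11 offers a painful-joint count, 5.2.3.1 links disease activity to erosive disease on X-ray, and the baseline list in 4.3 names neither pain nor disease activity.
- **Complete-case handling.** A patient with a known 6-month outcome but a missing baseline covariate would be dropped from the adjusted model.

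**Working it through.** **Inputs from the SAP.** Response 35% in both arms, margin 15 points, one-sided alpha 0.025, power 80%, 200 per arm, drop-out 20% (2.3, 2.4.3).

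**Assumed input.** R2 is the share of response variance explained by the three covariates. The SAP gives no value, so a range from 0 to 0.10 is shown.

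**Step 1: reproduce the sample size.** Completers needed per arm = (1.960 + 0.842)² × 2 × 0.35 × 0.65 / 0.15² = 158.7, so 159. Allowing for drop-out, 159 / 0.80 = 198.75, so 199 per arm or 398 in total, against 400 stated. The plan's figure reproduces. Expected completers are 200 × 0.80 = 160 per arm, or 200 × 0.75 = 150 at 25% drop-out.

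**Step 2: power with and without the covariates.** SE = sqrt(2 × 0.35 × 0.65 × (1 − R2) / n) and power = Φ(0.15/SE − 1.96). For n = 160 and R2 = 0, SE = 0.0533 and power = 80.3%.

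| Assumed R2 | 160 per arm (20% drop-out) | 150 per arm (25% drop-out) |
|---|---|---|
| 0 (same as centre-only) | 80.3% | 77.7% |
| 0.02 | 81.1% | 78.6% |
| 0.05 | 82.3% | 79.8% |
| 0.10 | 84.3% | 81.9% |

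At R2 = 0.10 the effective size is 160 / 0.90 = 178, about 18 extra completers per arm.

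**Step 3: simulation check of the formula.** Logistic outcome, three baseline covariates, standardised risk difference with an influence-function standard error, 6,000 replicates, Monte Carlo error about 0.5 point. Power, adjusted against centre-only:

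| Assumed R2 | 160 per arm | 150 per arm |
|---|---|---|
| 0 | 80.3 v 80.3% | 77.6 v 77.5% |
| 0.02 | 80.9 v 80.4% | 78.7 v 77.7% |
| 0.05 | 81.6 v 79.2% | 79.6 v 77.6% |
| 0.10 | 83.7 v 80.3% | 80.7 v 76.3% |

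A second simulation (3,000 trials per scenario, 160 per arm) compared the variance of the two estimators. The ratio of adjusted to centre-only was 1.004 at R2 = 0, 0.99 at about 0.03, 0.93 at about 0.07 and 0.88 at about 0.13. There was no material bias in the risk difference in any scenario.

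**Step 4: what missing covariates would cost.** Losing a share L of completers multiplies the variance by (1 − R2)/(1 − L), so the gain is gone when L = R2. With 5% lost, n = 160 × 0.95 = 152. Power is then 80.3% at R2 = 0.05 (no gain) and 79.1% at R2 = 0.02, below the centre-only 80.3%.

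**Step 5: can the model carry the covariates?** Expected responders are 320 × 0.35 = 112, enough for three more covariates.

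**The case against.** The strongest reply is that nothing here is wrong. The centre-only model is valid, includes the stratification factor, reports on the scale of the margin and matches the sample size calculation. Both analyses will be reported, so which is called primary could be seen as preference. That there is no error stands. But under 2.4.3 one interval decides the claim, so the label has a consequence.

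The benefit rests on an R2 that the SAP does not give, and finding predictors of improvement and response is itself an objective (1.2.2, 1.2.3). This stands, and it limits the claim to a probable gain. It is partly balanced by the near-absence of a penalty when the covariates predict nothing. Nor does adjustment reliably restore 80% at 25% drop-out: the figures for R2 of 0.02 and 0.05 stay just below it.

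Simulated power differs from the formula by up to about 1.4 points (76.3% against 77.7% for centre-only at 150 per arm in the R2 = 0.10 scenario), and the simulation did not use the SAP's bootstrap. The absolute levels are therefore approximate; the advantage of the adjusted model remains.

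The protocol may name the pain and disease activity measures. That is possible, and if so the SAP need only point to them. They become critical once they enter the deciding model.

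Exchanging primary and sensitivity analyses is safe only before outcomes are seen by arm. Parts of the SAP are in the past tense (2.7, 6.2) and 8.3 gives a project end of 31.12.2023, so timing is a real condition on the change.

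**Conclusion.** The point holds as a recommended improvement. The primary analysis is valid, and power is adequate on the plan's own inputs (80.3% at 160 completers per arm). Adding the three planned covariates keeps the same marginal risk difference, margin and decision rule. By formula it raises power by 0.8, 2.0 or 4.0 points at 160 per arm for R2 of 0.02, 0.05 or 0.10, and by 0.9, 2.1 or 4.2 points at 150 per arm. If the covariates do not predict response the gain is nil, at essentially no cost in precision.

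This rests on three conditions: an assumed R2, no completer lost through missing baseline covariates, and a change made before outcomes are seen by arm. Confidence in the size of the gain is moderate, because the SAP offers nothing from which to estimate R2.

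**What to change.** Amend the SAP before outcome data are seen by arm:

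1. **5.2.1.1:** make the primary model a logistic regression on arm, centre, baseline pain, baseline disease activity and baseline function (mean MAP-Hand score). Name the collected variable and its coding for each covariate, or cite where the protocol defines it.
2. **Estimator:** keep the standardised risk difference and the bootstrap interval as they are.
3. **5.2.1.5:** fill missing baseline covariate values by a simple imputation that ignores arm and outcome, for example the centre mean, recalculated in each bootstrap sample. No patient with a 6-month outcome is then dropped.
4. **2.4.3:** state that the decision is made on this interval.
5. **5.2.1.6:** keep the centre-only model as the sensitivity analysis.

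The cost is small. Both models are already planned and no new data are needed; the work lies in naming the covariates and programming one imputation rule. If the sponsor keeps the centre-only model as primary, the covariate definitions and the missing-value rule should still be fixed for the sensitivity analysis, so that it uses the same patients.
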